8.4.4. Vital Signs

Vital signs will include oral temperature (°C), respiratory rate (breaths per minute), heart rate (beats per minute [bpm]), and blood pressure (mmHg). Heart rate and blood pressure were collected in supine position and standing position at all scheduled time points.

Vital sign results and mean changes from baseline will be summarized by scheduled visit. It will also include the summary of last values on treatment and on study assessments. Potentially clinically significant values as outlined in [Table 11](#) will be summarized by treatment for

anytime on treatment, the last value on treatment and the last value on study. By-participant listing of vital signs will also be provided.

Table 11. Potentially Clinically Significant (PCS) Values for Vital Sign Parameters

Vital Sign	Units	Criteria for PCS Values (Observed values)		Criteria for PCS values (Change from Baseline values)	
		High	Low	Increase	Decrease
Heart rate (supine and standing)	Beats/min	>120	<40	NA	NA
Respiratory rate	Breaths/min	>20	<8		
Systolic blood pressure (supine and standing)	mmHg	>180	<90	≥30	≥30
Diastolic blood pressure (supine and standing)	mmHg	>110	<50	≥20	≥20
Supine – Standing* Systolic Blood Pressure	mmHg	≥20			
Supine – Standing* Diastolic Blood Pressure	mmHg	≥10			
Orthostatic hypotension: supine – standing* SBP and DBP	mmHg	SBP ≥20 and DBP ≥10			
Possible orthostatic hypotension: supine – standing* SBP and DBP	mmHg	SBP ≥20 or DBP ≥10			

* Supine – Standing means the difference of results between supine and standing positions.

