8.4. Safety Analysis

All safety summaries will be performed on the Safety Set using treatment received.

Safety and tolerability of SAGE-718 oral capsule in participants with PD-MCI is the secondary objective of this study and will be evaluated by the frequency and severity of TEAEs and withdrawal due to AEs. Other safety endpoints include change from baseline in vital signs, clinical laboratory analytes, ECGs, and [REDACTED].

The safety endpoints evaluated at scheduled visits are taken as done in nominal visit, without any windowing. If a value is available for a nominal scheduled visit, that value will be used in summary by visit. Unless specified, unscheduled measurement and ET measurement will be included only if a scheduled measurement is not available, and the unscheduled measurement and ET measurement falls within the visit window for the scheduled visit (same as WAIS-IV Coding Test in [Table 3](#)). If there are two or more measurements in a visit window, the measurement taken closest to the study day target will be used in analysis. If the two have same distance from the target study day, the latter one will be used.

Anytime on treatment, last value on treatment and last value on study will be included in the summaries, unless specified. Anytime on treatment is defined as measurement on or after first dose, on or before the date of last dose. Last value on treatment is defined as the last post-baseline value between first dose of IP and up to the date of last dose of IP (inclusive). Last value on study is defined as the last post-baseline value on or after the first dose of IP and on or before the last date of the study.

No statistical hypothesis testing will be conducted.

Safety data will be listed by treatment group and participant and summarized by treatment group.

Table 8. Summary of Safety Analysis

Safety Evaluation	Incidence	Source Data	Change from Baseline	Shift from Baseline	Potentially Clinically Significant	Abnormality/ Clinical Significance
AEs	X					
Clinical Laboratory		X	X	X	X	*
ECG		X	X		X	*
Vital Signs		X	X		X	
Physical Exam		*				

ECG = Electrocardiograms; [REDACTED]
X = Safety Assessment will be summarized in tables
* = Safety Assessment will be listed in individual participant data listings

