8.4.2. Clinical Laboratory

Any lab results considered clinically significant by the investigator will be captured as adverse events, hence will show up in AE displays.

For the laboratory results that are " $\leq x$ " or " $\geq x$ ", where x is a number as collected in the data, the numeric part of the result will be used in the calculation in the summary tables. If a laboratory value is reported as " $< y$ " then y minus the minimum value with the same precision as y (e.g., if y = 1.345, then use y - 0.001) will be used for the analysis. If a laboratory value is reported as " $> y$ " then y plus the minimum value with the same precision as y will be used for the analysis. The same is true if the result is presented as below limit of quantification (BLQ) and a lower limit of quantification (LLOQ) value is provided; the LLOQ value will be used for calculation in the summary tables. The actual results as collected will be displayed in the listings.

Results of continuous clinical laboratory parameters for hematology, biochemistry, coagulation, and urine samples for urinalysis at each scheduled visit and mean changes from baseline will be summarized in standard units. In addition, it will also include the summary of the last value on treatment and the last value on study.

Normal ranges for each parameter will be provided by the laboratory. Shift from baseline to post-baseline values in abnormality of hematology and biochemistry results will be

summarized. In addition, shift from baseline to worst post-baseline values in abnormality of results at any time on treatment, the last value on treatment (on or after first dose, on or before last dose) and the last value on study (after last dose, on or before last day of the study) will be summarized. If a participant has both low and high post-baseline records, the participant will be counted twice for each low and high cell.

Clinical laboratory results will be listed by participant and timing of collection for each treatment group.

The number and percentage of participants with potentially clinical significance (PCS) values for each laboratory parameter will be summarized by treatment for anytime on treatment, the last value on treatment and the last value on study. Sponsor determined PCS values will be identified for specific laboratory parameters as outlined in [Table 9](#) below.

Table 9. Potentially Clinically Significant Values for Specific Laboratory Parameters

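### SAP Table 11 counts orthostatic, heart-rate and respiratory-rate findings on treatment by observed value only, with no baseline count and no new-onset rule

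*SAP*

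**What the plan says.** SAP 8.4.4 summarizes the Table 11 PCS values by arm, covering "anytime on treatment, the last value on treatment and the last value on study. By-participant listing of vital signs will also be provided". SAP 8.4 defines the first of these periods purely by date: "Anytime on treatment is defined as measurement on or after first dose, on or before the date of last dose". Neither section requires that the criterion was unmet before dosing.

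Table 11 has two sets of criteria, one for observed values and one headed "Criteria for PCS values (Change from Baseline values". The second is filled in for systolic blood pressure (SBP, 30 mmHg or more in either direction) and diastolic blood pressure (DBP, 20 mmHg or more), supine and standing. It is marked not applicable for heart rate. It is empty for respiratory rate and for all four supine-minus-standing rows, including orthostatic hypotension ("SBP ≥20 and DBP ≥10") and the row labelled "Possible orthostatic hypotension: supine – standing* SBP and DBP" ("SBP ≥20 or DBP ≥10").

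Elsewhere in SAP 8.4.4, baseline enters through means: "Vital sign results and mean changes from baseline will be summarized by scheduled visit". Categorical shifts are planned for laboratory data (SAP 8.4.2: "Shift from baseline to post-baseline values in abnormality of hematology and biochemistry results will be" summarized). SAP Table 8 marks a shift for the laboratory row only. Appendix E lists two vital-sign tables, 14.3.6.1 (summary) and 14.3.6.2 (PCS), and no vital-sign shift table.

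The baseline information will exist. The protocol's Schedule of Assessments places orthostatic vital signs at Screening and Day 1, taken before the dose on dosing days, and again on Days 14, 42 and 70.

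**The concern.** The trial enrols people with Parkinson's disease, many of whom may take dopaminergic drugs, so some could have a postural drop at entry. The vital-sign exclusion in Protocol 7.2 (item 14b) concerns supine values, and no readable criterion screens on postural drop. A participant with the same drop on Day 1 predose and on Day 14 appears in Table 14.3.6.2 as an on-treatment case, and the table gives no means of separating that person from someone whose drop began after dosing.

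Two things are at stake. Persistent cases add to both arms and pull the ratio of on-treatment proportions towards 1, so a real new-onset signal is harder to see. In addition, a chance difference between arms at entry carries through and can be read as a treatment difference. Change from baseline in vital signs is a stated safety endpoint (SAP 4.2), and for these rows the categorical display does not refer to baseline.

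**Working it through.** The plan states no figure on this point, so there is none to reproduce. The check is a reading of Table 11, followed by an illustration with declared assumptions.

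**1. Which rows refer to baseline**

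| Table 11 row | Observed-value threshold | Change-from-baseline threshold |
|---|---|---|
| SBP, supine and standing | yes | ≥30 mmHg, either direction |
| DBP, supine and standing | yes | ≥20 mmHg, either direction |
| Heart rate | yes | not applicable |
| Respiratory rate | yes | empty |
| Four supine-minus-standing rows | yes | empty |

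**2. Does the standing-SBP change criterion cover new orthostatic cases?** Not always. Suppose supine SBP is unchanged and the postural drop goes from 5 to 25 mmHg. Standing SBP then falls by 25 − 5 = 20 mmHg. The participant newly meets the ≥20 postural row but not the ≥30 change criterion.

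**3. Share of counted cases that are pre-existing.** Let p be baseline prevalence, r the proportion of those positive again on treatment, and i new onset among the rest. None of these is in the documents. Assumed ranges: p 15–40%, r 60–80%, i 5–15%.

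On-treatment proportion = p·r + (1 − p)·i. Pre-existing share = p·r / [p·r + (1 − p)·i].

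- p = 0.15: lowest 0.090/(0.090 + 0.1275) = 41%; highest 0.120/(0.120 + 0.0425) = 74%.
- p = 0.30: lowest 0.180/(0.180 + 0.105) = 63%; highest 0.240/(0.240 + 0.035) = 87%.
- p = 0.40: lowest 0.240/(0.240 + 0.090) = 73%; highest 0.320/(0.320 + 0.030) = 91%.

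**4. Chance baseline imbalance.** SAP 5.2 gives about 76 randomized 1:1, so about 38 per arm. SD of the difference in baseline prevalence = √[2p(1 − p)/38]: 8.2, 10.5 and 11.2 percentage points at p = 0.15, 0.30 and 0.40. The part carried into the on-treatment comparison is this times (r − i), which runs from 0.60 − 0.15 = 0.45 to 0.80 − 0.05 = 0.75. That gives 8.2 × 0.45 = 3.7 points up to 11.2 × 0.75 = 8.4 points. Separately, for two independent Binomial(38, p) counts, the probability that the arms differ at entry by 4 or more participants (4/38 = 10.5 points) is 18% at p = 10% and 42% at p = 50%.

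**5. Dilution.** Assume r = 0.8 and true new onset of 5% on placebo and 20% on active, a ratio of 4.0 and a difference of 15 points.

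- p = 10%: placebo 0.08 + 0.9 × 0.05 = 12.5%; active 0.08 + 0.9 × 0.20 = 26.0%. Ratio 2.1, difference 13.5 points.
- p = 50%: placebo 0.40 + 0.5 × 0.05 = 42.5%; active 0.40 + 0.5 × 0.20 = 50.0%. Ratio 1.2, difference 7.5 points.

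Restricted to participants not meeting the criterion at baseline, the comparison is 5% against 20% at every p.

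**The case against.** The strongest reply is that this is a descriptive table in a randomized, placebo-controlled trial, and SAP 8.4 rules out hypothesis testing for safety. Pre-existing cases are equal across arms in expectation, and the risk difference shrinks only by the factor 1 − p, which is small if prevalence is low. This stands, and it limits the point to dilution and chance imbalance.

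Other outputs also help. SBP and DBP have change criteria. A vital-sign change becomes an adverse event if it leads to stopping or interrupting treatment, needs therapy, or is judged clinically significant (Protocol 11.2.1), and the TEAE definition counts a pre-existing condition only when it worsens. Listings 16.2.9.2.1 and 16.2.9.2.2 should allow baseline status to be recovered by hand. These points stand too, but a new postural drop judged not clinically significant can miss every summary, and a listing is not a planned comparison.

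Counting observed PCS values without a baseline condition is also common, and the SAP does it for most laboratory parameters (Table 9) and for the observed QTcF categories (Table 10). However, hematology and biochemistry also get shift tables, QTcF has change categories, and the investigator's ECG categories are shown at baseline. The orthostatic rows have none of these.

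Finally, enrolled prevalence cannot be known from the documents. Exclusion 13 is redacted, and exclusions 2 and 15 may remove some cases through comorbidity or cardiovascular disease. That is why the size is given only as a range.

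**Conclusion.** The point holds as a gap in presentation. For the orthostatic, heart-rate and respiratory-rate rows, Table 14.3.6.2 cannot separate findings present before the first dose from those that began on treatment. Under the assumed ranges, 41–91% of participants counted in an orthostatic row would be pre-existing cases, and a typical chance imbalance (one SD) would move the between-arm comparison by about 4 to 8 points. Both figures depend on the assumed prevalence, persistence and onset rates.

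Three stronger readings are tempting, and the documents do not support them:

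- That all PCS vital signs ignore baseline. SBP and DBP, supine and standing, have change-from-baseline criteria.
- That the orthostatic rows mostly record status at entry. The documents give no prevalence, and the assumed range itself starts below one half.
- That the table is biased. Randomization balances pre-existing cases in expectation, and no decision rule in the plan rests on this table.

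**What to change.** In SAP 8.4.4 and output Table 14.3.6.2, for the supine-minus-standing, heart-rate and respiratory-rate criteria:

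- Add a Baseline row, using the SAP 8.1 definition (last non-missing value before the first dose).
- For each of the three reporting periods, add the number and percentage meeting the criterion among participants who did not meet it at baseline.
- Keep the existing all-participant rows alongside.
- State which standing reading or readings (about 1 minute, 3 minutes, or both) define the drop, since Table 11's footnote does not say, and apply the same choice at baseline and after baseline.

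The cost is SAP wording and one additional block in one table, from data already scheduled. There are two downsides. The new-onset denominator is smaller: at the assumed 15–40% prevalence, 38 × 0.85 ≈ 32 down to 38 × 0.60 ≈ 23 per arm. And a single predose reading will misclassify some participants whose postural drop varies from day to day, which is a further reason to keep the all-participant rows.

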8.4.5. Physical Examination

A full physical examination is to be conducted during Screening and at Day 42 (End of Treatment). At other visits, an abbreviated physical examination will include a brief assessment of general appearance, cardiovascular, respiratory, gastrointestinal, and neurological systems, followed by a targeted physical assessment as determined by the investigator. Unscheduled, symptom directed examinations may be conducted at any time at the discretion of the investigator. Any baseline abnormalities will be recorded on the medical history form. Any post-baseline abnormalities or baseline conditions that worsened post-baseline will be recorded on the adverse events form.

The occurrence of a physical examination (yes/no) and the date performed will be listed by participant.

[REDACTED]

A large block of black redacted text, consisting of numerous horizontal lines of varying lengths, indicating that the content has been removed or obscured for privacy or security reasons.

[REDACTED]

[REDACTED]

[REDACTED]

[REDACTED]

[REDACTED]

[REDACTED]

[REDACTED]

[REDACTED]

8.4.7. Other Safety Analysis

Not applicable.

[REDACTED]

[REDACTED]

[REDACTED]

[REDACTED]

[REDACTED]

[REDACTED]

9. SUMMARY OF INTERIM AND DMC ANALYSES

Not applicable.

11. LIST OF APPENDICES

APPENDIX A. SCHEDULE OF ASSESSMENTS

APPENDIX B. DETAILS OF STATISTICAL METHODOLOGY

APPENDIX C. HANDLING OF MISSING DATES

APPENDIX D. CONVERSION FACTORS FOR CALCULATING LED

APPENDIX E. LIST OF TABLES, LISTINGS AND FIGURES

APPENDIX A. SCHEDULE OF ASSESSMENTS

Table 12. Schedule of Assessments

Assessments ^a	Screening Period	Baseline	Treatment Period				Follow-Up Period
	Days -28 to -8	Day -7 (±2 days)	Day 1 ^b	Day 14 (±2 days)	Day 28 ^c (±2 days) Phone Call	Day 42 ^d (-2 days)	Day 70 (±4 days) or ET
Informed consent ^e	X						
Inclusion/exclusion criteria	X	X	X				
Randomization			X				
Medical history and demographics ^f	X						
Participant training ^g	X	X					
Body weight	X		X			X	X
Body height	X						
Vital signs (including orthostatics) ^h	X		X	X		X	X
Physical examination ⁱ	X		X	X		X	X
FSH test ^j	X						
Serology test ^k	X						
12-lead ECG ^l	X			X		X	X

Assessments ^a	Screening Period	Baseline	Treatment Period				Follow-Up Period
	Days -28 to -8	Day -7 (±2 days)	Day 1 ^b	Day 14 (±2 days)	Day 28 ^c (±2 days) Phone Call	Day 42 ^d (-2 days)	Day 70 (±4 days) or ET
Clinical laboratory assessments ^m	X		X	X		X	X
Urine drug test	X		X	X		X	X
Alcohol breath test	X		X	X		X	X
Pregnancy test ^a	X		X				X
Optional biochemical research sample ^o	X			X		X	
Optional genetic research sample ^o	X						
Modified Hoehn and Yahr stage scale	X						

Assessments ^a	Screening Period	Baseline	Treatment Period				Follow-Up Period
	Days -28 to -8	Day -7 (±2 days)	Day 1 ^b	Day 14 (±2 days)	Day 28 ^c (±2 days) Phone Call	Day 42 ^d (-2 days)	Day 70 (±4 days) or ET
WAIS-IV Coding Test		X	X	X		X	X
[REDACTED] [REDACTED] [REDACTED] and PDAQ-15 Knowledgeable Informant) ^e		X				X	X

Assessments ^a	Screening Period	Baseline	Treatment Period				Follow-Up Period
	Days -28 to -8	Day -7 (±2 days)	Day 1 ^b	Day 14 (±2 days)	Day 28 ^c (±2 days) Phone Call	Day 42 ^d (-2 days)	Day 70 (±4 days) or ET
Daily mobile assessment ^t (DSST, PVT, sleep diary)					X		
IP self-administration ^u				X (once daily in the morning)			
IP dispensation ^v			X	X			
IP accountability/return ^w			X	X		X	
AEs/SAEs ^x	X	X	X	X	X	X	X
Prior and concomitant medications ^y				X			

Abbreviations: AE = adverse event; [REDACTED] COVID-19 = coronavirus disease 2019; [REDACTED]

[REDACTED] DSST = Digit Symbol Substitution Test; ECG = electrocardiogram; ET = early termination;
FSH = follicle-stimulating hormone; HIV = human immunodeficiency virus; ICF = informed consent form; IP = investigational product;

[REDACTED] PD = Parkinson's
Disease; [REDACTED]; PDAQ-15 KI = Penn Parkinson's Disease Activities Questionnaire-15
Knowledgeable Informant; [REDACTED]; PRO = patient-reported outcome; PVT = Psychomotor Vigilance Task; SAE = serious adverse event; [REDACTED]
[REDACTED] WAIS-IV = Wechsler Adult Intelligence Scale-IV.

^a The scales are to be administered after the daily dose of IP during the Treatment Period, and at approximately the same time of day (± 2 hours) throughout the study. For participants receiving medication for PD symptoms, the scales are to be administered in the "On" state (defined as the period in which motor symptoms are mitigated due to the effects of PD medication). For clinician administered scales, the same individual should administer the scale whenever possible.

^b All tests on Day 1 will be conducted predose.

^c Phone check-in only for AEs/SAEs and changes to medical history or medications.

^d Dosing ends on Day 42

^e Both participants and caregivers (if applicable) will be consented during the Screening Period.

^f In addition to full medical history, including family history of PD, all medications and supplements taken within 60 days prior to Screening, all medications used to treat PD regardless of timing, and all nonpharmacological methods (e.g., psychosocial, psychotherapeutic) used to treat or prevent [REDACTED], and cognitive manifestations of PD are to be recorded. Information regarding diagnosis, isolation, and/or hospitalization due to COVID-19 will be documented as part of medical history, AE collection, and prior/concomitant medication/procedure collection at Screening and throughout the study.

^g Participants and caregivers (if applicable) will be trained by study staff on the use of software applications and devices necessary for the conduct of the study.

^h Vital signs include body temperature, respiratory rate, heart rate, and blood pressure. Vital signs will be measured prior to dosing on days when IP is administered. Blood pressure and heart rate will be measured after the participant has been in the supine position for at least 5 minutes and then repeated approximately 1 and 3 minutes after standing, at all scheduled time points.

ⁱ A full physical examination will be conducted during Screening and at Day 42 (End of Treatment). At other visits, an abbreviated physical examination will include a brief assessment of general appearance, cardiovascular, respiratory, gastrointestinal, and neurological systems, followed by a targeted physical assessment as needed. A symptom directed examination may be conducted at any time at the discretion of the investigator.

^j Serum FSH test will be conducted at Screening for the female participants who are not surgically sterile to confirm whether female participants with ≥ 12 months of spontaneous amenorrhea meet the protocol-defined criteria for being postmenopausal.

^k To include hepatitis B and C screening tests, HIV-1 and -2 antibody.

^l A single ECG will be measured after the participant has been in the supine position for at least 5 minutes.

- ^m Clinical laboratory assessments will include blood samples for hematology, biochemistry, coagulation, and urine samples for urinalysis. Samples will be collected prior to dosing on days when IP is administered. On nondosing days, collection may occur at any time.
- ⁿ Serum pregnancy tests will be conducted for all female participants at Screening; urine pregnancy tests will be conducted at other scheduled time points for female participants who are not postmenopausal or surgically sterile.
- ^o Refer to [Table 13](#) for details.

^r PDAQ-15 Knowledgeable Informant is provided by caregiver.

^t Daily reminders will be sent to participants via a mobile device to complete assessments on remote device. Daily assessments include the [REDACTED] DSST, PVT, and the National Sleep Foundation Sleep Diary. It is recommended that assessments are completed at approximately the same time each day, within 1 hour following IP administration. Daily mobile assessments should be completed in a quiet area of participant's home. On dosing days the remote assessment will be completed in the clinic following dosing under observation by the study staff.

^u On Days 1, 14, and 42, the participants will self-administer IP in the clinic under the supervision of study staff. All scheduled safety assessments will be conducted prior to dosing and all scheduled cognitive tests will be administered postdosing.

^v Study staff will dispense enough IP for the participant to take daily at home until the next scheduled visit.

^w Participants will bring all used packaging and unused IP to the clinic at each visit for study staff to review and document.

^x AEs/SAEs collected from time of ICF throughout the duration of participation.

^y At Screening, to include all medications and supplements taken within 60 days and all medications used to treat PD regardless of timing. At subsequent visits, all changes to any medication should be captured.

Table 13. Schedule of [REDACTED], Biochemical, and Genetic Sampling

Assessments	Screening	Baseline	Treatment			Follow-Up
	Days -28 to -8	Day -7 (±2 days)	Day 1	Day 14 (±2 day)	Day 42 (-2 day)	Day 70 (±4 days) or ET
[REDACTED]						
Predose				X	X	X
Optional blood collection: biochemical research^b						
	X			X	X	
Optional blood collection: genetic research						
	X					

Abbreviations: ET = early termination; IP = investigational product; [REDACTED]

^bBiochemical samples will be collected at any time during Screening. On Days 14 and 42, the samples will be collected at times corresponding with the [REDACTED] blood draw.

